### **2.3 Tertiary/Exploratory/Correlative Objectives**

**Aim 3.** Determine preliminary effect size for BR+EX compared to EX on reducing soluble endothelial microparticles including, sICAM-1, sVCAM-1, sNCAM, MPO, IFN $\gamma$ , IL-1 $\beta$ , BDNF, TNF- $\alpha$ , and IL-10. Given the link between nitric oxide and regulation of NF- $\kappa$ B, it is reasonable that BR+EX may have synergistic properties that could contribute to

favorable effects on the vascular endothelium. As such, we anticipate a small to medium effect size in a beneficial direction for BR+EX compared to EX.

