### **3.0 Outcome Measures/Endpoints**

#### **3.1 Primary Outcome Measures**

Outcomes of interest include recruitment, retention, adherence (i.e., exercise prescription and assessments), perceived exercise difficulty, and adverse event rates. Project success will be based on 83% [20 of 24] of randomized participants completing 8 weeks of exercise training.

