#### **3.2 Secondary Outcome Measures**

**2a.** The distance (feet) covered during a 6-minute walk test at baseline prior to the intervention and following BR+EX is the main secondary outcome of interest. To confirm the relationship of the functional 6-minute walk test to aerobic fitness, measures of oxygen consumption (ml/kg/min or L/min), heart rate (bpm), and blood pressure (mm Hg) will be taken during constant speed walking at a typical walking pace prior to the 6-minute walk test. Additionally, functional mobility will be assessed by analyzing triaxial movement patterns from an accelerometer worn on the non-dominant hip during the 6-minute walk test.

The BR+EX intervention will be considered successful in the event that there is a statistically significant increase in 6-minute walk distance (feet) along with a decrease in oxygen consumption (ml/kg/min or L/min), decrease in exercising heart rate (bpm), improvement in heart rate recovery following exercise (post exercise heart rate – heart rate 1 min, 2 min after exercise (bpm)), decrease in exercising blood pressure (mm Hg), decrease in post-exercise blood pressure (mm Hg), and/or improvement in gait function (i.e. preferred walking speed, center of mass characteristics) from baseline to post-intervention above any improvement seen in EX.

**2b.** Percent changes in brachial artery diameter (%), cutaneous vascular conductance (%), and pulse wave velocity (m/s) at baseline prior to the intervention and following BR+EX are secondary outcomes of interest, representing changes in endothelial dependent vasodilation. A non-invasive technique of flow mediated dilation of the brachial artery using ultrasound imaging will be used to assess the percent change in vessel diameter following occlusion. A local heating protocol using non-invasive Laser Doppler flowmetry in conjunction with blood pressure measurements will be used to obtain measures of red blood cell (RBC) flux and mean arterial pressure (MAP) to calculate cutaneous vascular conductance (RBC flux/ MAP). The velocity of the pulse wave traveling from the carotid to femoral artery will be assessed non-invasively using tonometry.

A statistically significant increase in the percent change in brachial artery diameter (%), cutaneous vascular conductance (%), and/or a decrease in pulse wave velocity (m/s) in BR+EX above any improvement observed in EX from baseline to post-intervention will be considered a successful outcome.

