### 3.3 Tertiary/Exploratory/Correlative Outcome Measures

Tertiary outcome measures of interest include plasma concentrations of sICAM-1, s-VCAM-1, sNCAM, MPO, IFN $\gamma$ , IL-1 $\beta$ , BDNF, TNF- $\alpha$ , and IL-10 obtained from a venous blood sample taken at baseline and post-intervention.

Statistically significant decreases in endothelial microparticle concentrations from baseline to post-intervention in BR+EX that are above any decrease observed in EX will be considered a successful outcome.

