## 5.0 Study Design

To fulfill the purposes outlined above, a 2-arm randomized controlled study design will be employed. After completing initial screening procedures (**screening visit**), subjects will return

to the School of Public Health at Indiana University Bloomington to have baseline measures of weight, body composition, bone density, heart rate, cutaneous vascular conductance, blood pressure, assessed prior to and 3-hours following ingestion of beetroot juice (**Visit 1**). During this visit, two questionnaires will be administered to obtain information related to the health history, physical activity habits, mood state, and cognitive abilities of the subjects. Following a minimum 7-day washout period, to mitigate the risk of any carry-over effect from the acute dose of beetroot juice administered during the initial visit, subjects will have their blood drawn at the Indiana University Student Health Center followed by measures of weight, body composition, and pulse wave velocity performed at the School of Public Health at Indiana University Bloomington (**Visit 2**). During this visit they will also perform two 6-minute walking tests, and muscle function test. After baseline assessments **Visits 1-2**, participants will be randomly assigned to one of two study arms. All study arms will complete an 8-week exercise training protocol. The first arm will serve as a control group and will require participants to only complete the 8-week exercise training protocol (EX). The second arm will complete exercise training with ingestion of a beetroot (BR+EX). Exercise training will occur no more than 6 weeks following baseline Visit 2 to minimize the effects of potential changes in physical conditioning/deconditioning on baseline measures. Subjects will be asked to repeat baseline Visit 2 before initiating exercise training in the event >6 weeks lapses from the completion of the final baseline assessment visit.

The same procedures as performed in **Visits 1-2** will be repeated following the treatment intervention for **Visits 3-4** in reverse order. The procedures outlined for **Visit 2** will be performed during **Visit 3**, and procedures for **Visit 1** for **Visit 4**.

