Based on participant responses to the questions, research personnel will determine preliminary eligibility for an on-site visit. If it appears the participant meets the preliminary eligibility, an on-site visit will be scheduled, and a consent form will be mailed / emailed to the participant for their consideration and review. After the study participant has had several days to review the consent form, research personnel will call the participant to answer any further questions regarding the consent form. Participants will be enrolled in small ( $n = 9$ ) cohorts or "waves" to facilitate social support and adherence to the supervised exercise training sessions. We anticipate having 9 waves to successfully reach our target  $n$ . This assumes that each wave will have 4 participants, hence, 4 participants x 9 waves = 36 total participants.

At the on-site screening visit, research personnel will once again cover inclusion/exclusion criteria, study procedures, requirements, and risks. Following written informed consent, participants will have their body weight and standing height measured to determine their body mass index (i.e., 25.0-39.9 kg/m^2). Current prescription drug use will be recorded by having

participants physically bring their prescription labels or medication bottles to the testing site. Additionally, participants will complete a Medical History Questionnaire (see attachments).

Written authorization will be obtained from consented participants to allow research personnel to contact the participant's primary care physician to receive physician's clearance prior to study testing visits. The physician will be asked to provide their assent or dissent for their patient to participate in the exercise testing protocols and supervised group exercise sessions involved with this study. They will have the option to indicate any modifications that may be necessary for the patient to participate safely. The Physician Clearance Form (see attachments) will be faxed to the patient's physician following the screening visit.

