### **12.0 Statistical Considerations**

Rather than confirm efficacy, this proposal addresses elements of feasibility such that we intend to generate preliminary effect sizes for a larger-scale investigation. Descriptive statistics and calculation of rates (e.g., recruitment, retention, adherence, and adverse event) will be used for study aim 1. Between-group differences in descriptive data along with aims 2(a,b) and 3 will be evaluated using an unpaired t-test. Effect size calculations will be performed with Cohen's  $d$  to qualify substantive differences: small (0.2), medium (0.5), and large (0.8). Potential covariates of interest include age, body mass, body fat percentage, and/or markers of inflammation. Non-normally distributed data will be log-transformed. Two-tailed parametric correlations (Pearson) will be performed and based on consequent results, multiple linear regression will be used to examine changes in inflammation, endothelial function, distance in 6-minute walk test, leg strength, and resting blood pressure/arterial stiffness.

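### Read literally, the Aim 3 success rule tests the change within BR+EX and only compares it numerically with EX, which does not match the between-arm t-test planned in Section 12

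*Combined protocol and SAP*

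**What the plan says.** Section 3.3 sets the Aim 3 criterion, which covers nine plasma markers: "Statistically significant decreases in endothelial microparticle concentrations from baseline to post-intervention in BR+EX that are above any decrease observed in EX" count as success. Section 3.2 (2b) has a similar construction for the vascular outcomes, asking for a statistically significant improvement "in BR+EX above any improvement observed in EX from baseline to post-intervention will be considered a successful outcome". The 2a rule for the 6-minute walk is a composite that also ends by requiring improvement beyond that in EX.

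The objective is comparative. Section 2.3 reads "Determine preliminary effect size for BR+EX compared to EX on reducing soluble endothelial microparticles". Section 12.0 names the test: "Between-group differences in descriptive data along with aims 2(a,b) and 3 will be evaluated using an unpaired t-test". It does not say whether the tested variable is the change or the post-intervention value, and it does not link the test to the success statements in Section 3. No paired or within-arm test is planned anywhere.

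On design, Section 5.0 states: "All study arms will complete an 8-week exercise training protocol". On purpose, Section 12.0 states: "Rather than confirm efficacy, this proposal addresses elements of feasibility".

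**The concern.** In Section 3.3 the words on significance attach to the decrease from baseline inside BR+EX. EX enters as a decrease to be surpassed, and the sentence requires no test of the difference. Someone applying it as written could find no between-arm difference under Section 12.0 and still record a success for juice.

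A before-after test within BR+EX cannot separate juice from the training both arms receive. If training alone lowers a marker, BR+EX will tend to show a significant fall. By symmetry it will also show the larger mean fall in half of all trials, even if juice is inert. A label obtained that way would not answer the BR+EX versus EX question, and Section 1.0 says the findings could inform a larger trial.

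**Working it through.** The plan gives no alpha, power or error rate for Aim 3, so there is no figure of its own to reproduce. The check sets out what the literal rule would do.

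**Inputs from the documents**
- Sample size, first figure (Section 3.1): "Project success will be based on 83% [20 of 24] of randomized participants completing 8 weeks of exercise training". 20/24 = 83.3%. With equal allocation (Section 6.0), 24/2 = 12 per arm randomized and 20/2 = 10 per arm completing.
- Sample size, second figure (Section 6.0): "4 participants x 9 waves = 36 total participants", so 36/2 = 18 per arm. The two totals disagree, which is a separate matter; all three arm sizes are used here.
- Scale for effects (Section 12.0): Cohen's d of 0.2, 0.5 and 0.8.

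**Assumptions**
- Two-sided 5% tests. Section 12.0 specifies two-tailed only for the correlations.
- Normal changes with equal SD in both arms.
- No juice effect.
- The same mean improvement d in both arms, in units of the SD of change. The documents give no value for d, so a range is shown.

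**Rules compared**, with D̄ the mean improvement, s the SD of change and n the number per arm
- Literal Section 3.3 rule: D̄(BR+EX) / (s/√n) exceeds the 97.5% point of t on n − 1 df, and D̄(BR+EX) > D̄(EX).
- Section 12.0 test applied to change: [D̄(BR+EX) − D̄(EX)] / √[(s²(BR+EX) + s²(EX))/n] exceeds the 97.5% point of t on 2n − 2 df.

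**False success per marker** (200,000 simulated trials per cell)

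| Shared change d | Literal, n = 10 | Literal, n = 12 | Literal, n = 18 | Between-arm test, any n |
|---|---|---|---|---|
| 0 | 2.4% | 2.4% | 2.5% | about 2.5% |
| 0.2 | 7.6% | 8.6% | 11.3% | about 2.5% |
| 0.5 | 23.9% | 27.8% | 37.3% | about 2.5% |
| 0.8 | 40.9% | 44.9% | 49.3% | about 2.5% |

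The literal rule has a ceiling of 50%: once the within-arm test is nearly always significant, only the coin-flip of which arm has the larger mean remains. The between-arm rate does not depend on d because the shared change cancels in the difference.

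**Nine markers.** Section 3.3 does not say how many must succeed. If any one were enough (n = 12, assumed correlation 0.3 between markers; 40,000 trials), the literal rule gives 17%, 44% and 83% at d = 0, 0.2 and 0.5. The between-arm test gives about 17% at each.

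**Power of the between-arm test** (normal approximation), Φ(δ√(n/2) − 1.96) for a juice effect δ. At δ = 0.5:
- n = 10: Φ(1.118 − 1.96) = 20%
- n = 12: Φ(1.225 − 1.96) = 23%
- n = 18: Φ(1.500 − 1.96) = 32%

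At δ = 0.2 it is 7-9%.

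**The case against.** The strongest reply is that the plan already contains the right test. Section 12.0 evaluates Aims 2 and 3 by an unpaired between-group comparison, Section 2.3 frames Aim 3 as one arm against the other, and the paired test simulated above is named nowhere. Read together, these sections allow Section 3.3 to mean a significant excess over EX. If the Section 12.0 test must also be met, false success cannot exceed about 2.5% per marker. This stands in part: a reader might infer that the plan judges juice only by the change within BR+EX, and the documents do not support that. What remains is that Section 12.0 sets no success criterion and Section 3.3 does not refer to it, so nothing says which governs.

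The Section 3.2 wording reads at least as naturally as a between-arm excess, and 2a is a composite to which the per-marker rates do not apply. Both points stand; Section 3.2 is ambiguous rather than wrong. Nor should a practice effect on the 6-minute walk be taken for granted, since Section 5.0 schedules two walks at Visit 2.

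A reader might also infer that training gains would often be scored as juice gains. The documents give no training effect for any of the nine markers, and Section 1.0 says postmenopausal women respond less to training. At 0.2 SD the rate is 8-11%. How often it would happen is therefore unknown.

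Finally, project success rests on completion of training, and what passes to the larger study is effect sizes, which the success wording does not alter. This stands and limits the consequence.

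**Conclusion.** The point holds as a mismatch between a stated success rule and the planned test. Followed literally, Section 3.3 can credit juice with a change that training produced in both arms. With no juice effect, the false-success rate per marker runs from about 2.5% with no shared change to 41-49% at 0.8 SD for 10 to 18 per arm, against about 2.5% for the between-arm test. These figures rest on two-sided 5% tests, normal changes with equal SDs, and a shared training change that the documents do not supply. They apply only if the literal wording is used in place of the Section 12.0 comparison.

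The consequence is a possibly misleading success label on tertiary, and possibly secondary, outcomes. The feasibility conclusion is unaffected, and the study does not set out to confirm efficacy. The correction is still worth making before analysis, because the text leaves two incompatible ways to declare success.

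**What to change.** In Section 3.3, and for clarity in Section 3.2, define any success statement on the between-arm difference in change from baseline (BR+EX minus EX). Judge it by the unpaired comparison already planned, and say in Section 12.0 that the comparison is applied to change and at what alpha. Report the estimate and Cohen's d, each with a 95% interval. Add a sentence that before-after tests within an arm support no success claim.

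This is a wording change and needs no new data, visits or participants. The cost is that fewer outcomes will meet the success wording: between-arm power is only about 20-32% at d = 0.5, so the interval should carry the interpretation. The 2.5% rate is per outcome and does not cover multiplicity. If a success label is kept for Aim 3, Section 3.3 should also say how many of the nine markers must meet it.

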## 4.0 Eligibility Criteria

### 4.1 Inclusion Criteria

- Post-menopausal women (self-report)
- Ages 75 and younger (confirmed by birth date listed on participant's driver license at screening visit)
- Physician's clearance for study participation (required prior to baseline testing)
- English-speaking
- Body mass index between 25.0 to 39.9 kg/m^2 (measured on-site at screening visit)
- Able to ambulate without assistance

### 4.2 Exclusion Criteria

[figure not shown]
- Unable to provide informed consent
- < 18 years or > 75 years of age (confirmed by birth date listed on participant's driver license at screening visit)
- Body mass index < 25.0 or >39.9 kg/m^2 (measured on-site at screening visit)
- Greater than stage II hypertension (i.e. >159/99 mm Hg)
- Current smoker (self-report)
- Currently pregnant, lactating, or trying to become pregnant (self-report)
- Habitually exercise training  $\geq$  3 times per week (self-report)
- Significant orthopedic limitations or other contraindications to strenuous exercise
- Live or work >50 miles from Bloomington study site or do not have transportation to the study site
- Anticipate elective surgery during the study period
- Plan to move residence or travel out of the local area during the study period
- Current use of anti-coagulants (e.g. Coumadin or Warfarin)
- Current use of prescription medications that affect heart rate or blood vessel dilation (e.g. phosphodiesterase-5 inhibitors, proton pump inhibitors, systemic  $\beta$ -adrenergic blockers, nitrates, calcium channel blockers, hormone replacement therapy) (self-report and confirmed on-site at screening visit)
- Psychological or social characteristic that would interfere with their ability to fully participate in the study (i.e. taking longer than allowed time to complete cognitive assessments)

## 5.0 Study Design

To fulfill the purposes outlined above, a 2-arm randomized controlled study design will be employed. After completing initial screening procedures (**screening visit**), subjects will return

to the School of Public Health at Indiana University Bloomington to have baseline measures of weight, body composition, bone density, heart rate, cutaneous vascular conductance, blood pressure, assessed prior to and 3-hours following ingestion of beetroot juice (**Visit 1**). During this visit, two questionnaires will be administered to obtain information related to the health history, physical activity habits, mood state, and cognitive abilities of the subjects. Following a minimum 7-day washout period, to mitigate the risk of any carry-over effect from the acute dose of beetroot juice administered during the initial visit, subjects will have their blood drawn at the Indiana University Student Health Center followed by measures of weight, body composition, and pulse wave velocity performed at the School of Public Health at Indiana University Bloomington (**Visit 2**). During this visit they will also perform two 6-minute walking tests, and muscle function test. After baseline assessments **Visits 1-2**, participants will be randomly assigned to one of two study arms. All study arms will complete an 8-week exercise training protocol. The first arm will serve as a control group and will require participants to only complete the 8-week exercise training protocol (EX). The second arm will complete exercise training with ingestion of a beetroot (BR+EX). Exercise training will occur no more than 6 weeks following baseline Visit 2 to minimize the effects of potential changes in physical conditioning/deconditioning on baseline measures. Subjects will be asked to repeat baseline Visit 2 before initiating exercise training in the event >6 weeks lapses from the completion of the final baseline assessment visit.

The same procedures as performed in **Visits 1-2** will be repeated following the treatment intervention for **Visits 3-4** in reverse order. The procedures outlined for **Visit 2** will be performed during **Visit 3**, and procedures for **Visit 1** for **Visit 4**.

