**Pulse Wave Velocity (PWV)**- Measurements of PWV (m/s) will be obtained from standard blood pressure and tonometry assessment using the ATCOR SphygmoCor device. This device is a non-invasive way to perform central blood pressure waveform assessment. During **Visits 2 and 2**, subjects will be asked to lie still in a supine position on a padded table surface for a duration of 10 minutes. A leg blood pressure cuff will be placed on the upper thigh. A technician will apply carotid tonometry simultaneously to inflating the blood pressure cuff to obtain blood pressure waveforms at the carotid and femoral artery sites. SphygmoCor software uses physical distance measurements between the sites to calculate velocity.

**Laser Doppler Blood Flow Heating Protocol**- Laser Doppler (Blood FlowMeter, Ad Instruments) will be used to assess cutaneous vascular conductance in response to a localized heating stimulus. Two small skin surface probes will be applied to the non-dominant forearm of the subject during **Visits 1 and 4**. Resting measurements will be obtained for 5 minutes followed by a measure of resting blood pressure. Localized skin heating will be accomplished with local heating units that will surround the skin surface probes of the laser Doppler. Both probes will be heated to a set temperature of 39°C (102°F) for 25 minutes. . The temperature of the probes will then be increased until a maximum temperature of 44°C (111°F) and held for 15 minutes . Blood pressure measurements will be obtained from the dominant arm every 10 minutes during the 40-minute heating protocol. From measures of blood pressure and the laser Doppler blood flow, cutaneous vascular conductance will be calculated as a ratio of skin blood flow to mean arterial pressure. Cutaneous vascular conductance will be expressed as a percentage of maximal conductance measured at the end of the heating protocol.

**Blood Pressure**- Blood pressure readings (mm Hg) of systolic and diastolic blood pressure will be taken using an automated sphygmomanometer on the dominant upper arm. During **Visits 1 and 4**, measurements will be taken during seated rest, every 10 minutes during the localized heating protocol, and every hour for 3-hours following ingestion of beetroot juice. During **Visits 2 and 3**, measurements will be taken during standing rest prior to the submaximal walking exercise, at minutes 3 and 5 during submaximal walking, and after 3 minutes of recovery following submaximal walking.

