## **8.0 Study Calendar**

(Screening Visit) After obtaining consent, subjects will be asked to complete a health history questionnaire, risk factor stratification document indicating their readiness to exercise, and provide information to obtain permission to contact their primary care physician. Their age will be verified by a member of our research team by having them provide a valid photo ID (e.g. driver's license), and current prescription medications will be verified by having them bring-in their medication bottles or labels. A measure of height and weight (via BIA) will be obtained to verify BMI inclusion criteria of 25.0 to 39.9 kg/m^2.

(Visit 1) All procedures during this visit will take place at the School of Public Health, Indiana University Bloomington. Measures of height, weight (BIA), body composition (BIA/DEXA), total body water (BIA), and bone density (DEXA) will be taken after having participants change into a provided standard set of hospital scrubs. The remaining procedures will be conducted with the participant resting quietly on a reclining couch. They will be outfitted with a chest-strap electrocardiograph monitor for the duration of the visit. Two laser Doppler probes will be attached to their non-dominant forearm while a localized heating protocol is initiated. A blood pressure cuff will be affixed to their dominant upper arm and blood pressure will be assessed after 5 min of seated rest, and at every 10 minutes of the 30-minute heating protocol. Following, they will perform a breath analysis to measure pre-ingestion levels of exhaled nitric oxide before ingesting 140mL of a commercial beetroot juice supplement. During a 3-hour window following ingestion, participants will be given a rest period and asked to complete a set of two questionnaires. During this time, blood pressure and methemoglobin using a fingertip pulse oximeter will be assessed once every hour. They will be asked to perform an additional breath analysis 3-hour post-ingestion to coincide with estimated maximum nitric oxide bioavailability provided by the supplement. After which, a repeat of the localized heating protocol and blood pressure measurements will be performed.

(Visit 2) A venous blood sample will be collected at the Indiana University Student Health Center. Following, all remaining procedures will take place at the School of Public Health, Indiana University Bloomington. Participants will again, be asked to change into a provided

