standard set of hospital scrubs so that accurate measurements of body weight (BIA) and composition (BIA) can be obtained. They will then be asked to lie supine while resting quietly for a period of 10 minutes on a padded table while measures of pulse wave velocity are obtained. They will then be escorted to the recreational track within the School of Public Health building to complete the 6-min walking test and muscle function test.

(8-weeks Supervised Exercise Training) After being randomized into either an exercise only (EX) or beetroot and exercise (BR+EX) group, subjects in the BR+EX group will receive a 4-week supply of beetroot juice. They will additionally be asked to attend 3 sessions of supervised exercise training at CrossFit, Bloomington for a duration of 8 weeks. Subjects in BR+EX will be instructed to consume the beetroot juice 3 hours prior to each attended exercise session.

(Visits 2-3) The remaining follow-up visits will follow the exact same procedures as outlined for Visits 1-2 and will be performed in the reverse order.

	Screening	Initial Assessments		Exercise Training Intervention	Follow-up Assessments	
	Time point 0	Visit 1 (as scheduled)	Visit 2 (following  7-day washout period)	0 to 8 weeks (following £ 6 weeks)	Visit 1 (following  2 days)	Visit 2 (following  2 days)
STUDY PROCEDURES						
Obtain Consent	X					
Medical History Questionnaire	X					
ACSM Risk Factor Stratification	X					
Obtain Permission to Contact Physician	X					
Verification of Age (driver's license)	X					
Prescription Medication Verification	X					
Height	X	x				X
Body Weight (BIA)	X	x	X		X	X
Body Fat Percentage (BIA)		X	X		X	X
Total Body Water (BIA)		X	X		X	X
DEXA		X				X
Heart rate (Actiheart)		X		X		X
Localized Heating Protocol using Laser Doppler		X				X
Blood Pressure		X				X
Nitric Oxide Breath Analysis		X		X		X
Acute Administration of Beetroot Juice (140 mL)		X				X
Blood Oxygen/ Methemoglobin Oximetry		X				X
Questionnaire (Part A and B)		X				X
Venous Blood Draw			X		X	
Pulse Wave Velocity			X		X	
Submaximal Walk Test			X		X	
Heart rate (chest-strap)			X		X	
Accelerometry			X		X	
6-minute Walk Test			X		X	

Rates of Exertion (continuous analog scale)			X		X	
Rates of Exertion (discrete analog scale)			X	X	X	
Isokinetic Dynamometry			X		X	
Supervised Exercise Training Sessions				X		
24hr Dietary Recall				X (3 during week 1 and 3 during week 8 of supervised exercise training)		

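### The plan does not say which skin blood-flow (CVC) reading, before or after the test dose of juice, is the secondary 2b outcome

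*Combined protocol and SAP*

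**What the plan says.** **Two readings per visit.** Section 5.0 lists CVC among the Visit 1 measures "assessed prior to and 3-hours following ingestion of beetroot juice". The Visit 1 text in Section 8.0 agrees: after the 3-hour breath test, "a repeat of the localized heating protocol and blood pressure measurements will be performed".

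**Both arms, both visits.** Visit 1 comes before randomization, so everyone is dosed there. Section 5.0 then states: "The procedures outlined for Visit 2 will be performed during Visit 3, and procedures for Visit 1 for Visit 4". The Section 8.0 calendar marks the 140 mL acute dose at the initial Visit 1 and in the second follow-up column, which carries the Visit 1 procedures, with no restriction by arm. Exercise-only (EX) participants therefore also drink juice before their second Visit 4 reading. Each participant who completes follow-up has four CVC readings.

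**The outcome.** Section 3.2 names "Percent changes in brachial artery diameter (%), cutaneous vascular conductance (%), and pulse wave velocity (m/s) at baseline prior to the intervention" and following the intervention as secondary outcomes. That wording separates baseline from training; it does not separate pre-juice from post-juice. Section 7.0 gives the scale: "Cutaneous vascular conductance will be expressed as a percentage of maximal conductance measured at the end of the heating protocol". It says nothing on which reading is used.

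**The analysis.** Section 12.0 specifies an unpaired t-test for Aims 2a, 2b and 3. It names neither a CVC reading nor a change score. Its list of possible covariates does not include baseline CVC. Section 3.2 counts 2b a success if BR+EX improves significantly more than EX on brachial diameter, CVC and/or pulse wave velocity.

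**The concern.** The pre-juice change compares 8 weeks of training with juice against 8 weeks of training without it. The post-juice change compares two trained arms that have both just had the same dose. These are different quantities, and the plan does not say which one its CVC effect size will describe.

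Two things are at stake. Section 12.0 says the pilot exists to generate effect sizes for a larger study, and an effect size whose measurement is not fixed serves that purpose poorly. Also, success is judged by statistical significance under an and/or rule, so leaving the reading open allows the more favourable one to be reported.

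CVC carries some weight here. Flow-mediated dilation, the measure named in Aim 2b, is described in Section 3.2 but has no procedure entry in Section 7.0 and no row in the calendar. CVC and pulse wave velocity are the 2b measures actually scheduled.

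**Working it through.** The plan gives no sample size, power or alpha for CVC, so there is no figure to reproduce.

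**Inputs.** Arm sizes: 12 per arm (24 randomized, Section 3.1) or 18 per arm (36, Section 6.0). Expected effect: small to medium (Section 2.2), that is d = 0.2 to 0.5 (Section 12.0 labels). Assumed, because the documents do not give them: two-sided alpha 0.05 for the arm comparisons, the correlations between readings, and the size of the acute effect.

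**1. Can a direction of bias be stated?** Let T be an arm's mean pre-juice change, and a1 and a4 its mean acute effect at Visits 1 and 4.

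- Pre-juice contrast: T(BR+EX) − T(EX).
- Post-juice change in one arm: T + a4 − a1.
- Randomization makes a1 equal between arms in expectation, so the post-juice contrast is the pre-juice contrast + [a4(BR+EX) − a4(EX)].

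If the acute effect is the same in both arms, the bracket is zero and the contrasts agree. Write the post-juice contrast as d × (1 − s), with the SD held fixed:

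| s | d = 0.2 | d = 0.5 |
|---|---|---|
| −0.5 (BR+EX responds more) | 0.30 | 0.75 |
| 0 (additive) | 0.20 | 0.50 |
| 0.5 (EX responds more) | 0.10 | 0.25 |
| 1 | 0 | 0 |

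The documents give neither the sign nor the size of s.

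**2. What does the free choice cost in false positives?**

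- One named outcome: 5%.
- Either of two uncorrelated tests: 1 − 0.95² = 9.75%.
- Simulation of 20,000 null trials per setting, with four equally correlated readings (r = 0.3 to 0.7) and 12 or 18 per arm: 9.4 to 10.1% for the pre-pre or post-post change. Equal correlation makes these two changes uncorrelated, so this matches 9.75% within simulation error.
- If readings within a visit correlate more strongly than readings across visits, the two changes are positively correlated and the rate lies between 5% and 9.75%.
- Adding two more candidates (change in the acute response; pre-juice Visit 1 to post-juice Visit 4) gives 14.5 to 15.5% in the same simulation.
- These rates count both directions. In the favourable direction alone, 2.5% becomes 1 − 0.975² = 4.9%.

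**3. What does it cost in the effect size?** If the two true effects are equal and the larger estimate is reported, the expected upward bias for uncorrelated estimates is SE/√π = 0.564 × SE, with SE of d ≈ √(2/n).

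- n = 12 per arm: 0.408 × 0.564 = 0.23.
- n = 18 per arm: 0.333 × 0.564 = 0.19.

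Positive correlation ρ between the estimates multiplies this by √(1 − ρ).

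**4. What does ANCOVA gain?** With equal variances at both visits and pre-post correlation r, the variance is proportional to 2(1 − r) for a change score and 1 − r² for ANCOVA. The ratio is (1 + r)/2:

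- r = 0.3: 0.65, or 35% lower.
- r = 0.5: 0.75, or 25% lower.
- r = 0.7: 0.85, or 15% lower.

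The cost is one degree of freedom: 22 to 21 with 12 per arm, or 34 to 33 with 18.

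**The case against.** A reader might infer that the post-juice reading must shrink the contrast, because the control arm has had juice too. The documents do not support that. Both arms take the same dose at both visits, so an additive acute effect cancels. Shrinkage needs EX to respond more than BR+EX at Visit 4, for instance through a ceiling on a percent-of-maximum scale. If BR+EX responds more, the contrast grows. The calendar also appears to put a 2-day interval before each follow-up visit (the sign is garbled), so the pre-juice Visit 4 reading may carry no acute advantage for EX to catch up on. This objection stands in full, and no bias figure is claimed.

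It can also be said that preferring the pre-juice reading is partly judgement, since Section 1.0 speaks of effects that juice acutely elicits. That stands in part. A sponsor could argue for the post-juice reading, but would still have to name it in advance. The pre-juice reading is the one at which EX has not just been given juice, which fits the BR+EX against EX comparison of Aim 2b.

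Finally, CVC is one secondary measure in a feasibility pilot that disclaims confirming efficacy, and project success rests on completion. That limits the severity. It does not remove the point, because Section 3.2 still declares success by significance and Section 12.0 promises effect sizes.

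**Conclusion.** The point holds in a limited form. CVC is a named outcome, but the reading and the change score are not named, and the two readings define different comparisons. The firm consequence is selection. Choosing between the two changes raises the CVC false-positive rate from 5% to about 9 to 10%, assuming two-sided alpha 0.05 and uncorrelated changes, and by less if they are positively correlated. Reporting the larger estimate could add about 0.2 to d on the same assumptions, as much as the small effect the plan hopes to detect. The documents do not show that anyone intends to choose after seeing the data; the plan simply does not rule it out. The point does not threaten the primary feasibility aim, but it should be closed before analysis.

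**What to change.** In Section 3.2, name pre-ingestion CVC at Visit 4, as a percentage of maximal conductance, as the CVC outcome. It stands alongside the other 2b measures and does not replace them. Label the post-juice reading and the acute response (post minus pre) exploratory.

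In Section 12.0, replace the unpaired t-test for CVC with ANCOVA: Visit 4 pre-ingestion CVC on arm, adjusted for Visit 1 pre-ingestion CVC. Report the adjusted difference with its 95% confidence interval, and state which SD is used for Cohen's d.

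The cost is a short edit to each section and one degree of freedom. All readings are already scheduled, so no new data are needed.

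While editing, reconcile the length of the heating protocol, which is 40 minutes in Section 7.0 and 30 minutes in the Visit 1 text of Section 8.0. The maximum measured at its end is the CVC denominator.
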